12.8.1 Figure 2: ChangeToOne Power Analysis; Alternative Cases

We use LSMEANS to aid intuition concerning the precision to expect from these analyses. For the current application, the LSMEAN statement estimates, for each arm separately, the probability of success at the average time (roughly month 22). More specifically, this is a transform of a linear combination of the fixed effects. Random site effects are taken into account (via the variance of the estimated betas) when calculating confidence limits. Figure 3 shows the estimated probability, with 95% confidence intervals, for the baseline arm (black solid) and the IF arm (red dashed). The point estimates and confidence limits are averaged across the iterations of the simulation. Increasing ICC widens the confidence intervals considerably.

12.8.2 **Figure 3: ChangeToOne Confidence Intervals for p1, p2; Alternative Cases**

[figure not shown]

Figure 4 gives simulated test size (i.e. under the null hypothesis) at $\alpha = 0.05$, 1-tailed for the last 3 scenarios of Table 4, calculated on the basis of 10,000 iterations. A horizontal reference line marks 0.05, and the Y-axis scale goes from 0 to 0.1. Test sizes are tolerable, if not perfect.

12.8.3 **Figure 4: “ChangeToOne” test size; Null Cases**

[figure not shown]
[figure not shown]

Figure 5 gives LSMEAN estimates of the probabilities of success in the “null” scenarios of Table 4. As expected, the two arms agree as to success probabilities in this case. Again, increasing ICC widens the confidence intervals.

12.8.4 **Figure 5:** “ChangeToOne” Confidence Intervals, p1, p2; Null Cases

12.9 Bayesian Approach

We also considered a Bayesian approach, which has its own attractions and drawbacks. We detail these in an Appendix Bayesian Analysis. We propose to use the “ChangeToOne” approach for the primary analysis, and relegate the Bayesian approach to a secondary supporting analysis that we do not discuss here.

12.9.1 Summary of Power Simulations

Under the most optimistic scenarios investigated (Implementation Outcome with low p_1 and Efficacy Outcome with high p_2) and $ICC < 0.3$ (and perhaps higher), power for the envisioned design exceeds 0.8 under the ChangeToOne policy and Bayesian approach. Other scenarios featuring less separation between groups have lower power.

Having sites with “all zeros” in the baseline arm degrades power if you take no corrective action. The “ChangeToOne” policy seems a simple and attractive remedy.

A Bayesian approach with diffuse priors leads to conclusions similar to those from the ChangeToOne policy (see Appendix Bayesian Analysis).

Except for the credibility intervals for $p_2 - p_1$, increasing ICC degrades precision.

12.10 Missing Data

Patients lost to follow-up will not be counted as successes for either primary outcome, and, because counted as failures, will not generate missing data. Accordingly, we ignore the possibility

of loss to follow-up in the power calculations, and will assume that losses are failures for the purposes of the actual data analysis.

Several strategies will be implemented to minimize the likelihood and the rate of potential missing data in the proposed study. Timely data entry combined with frequent, planned, and scheduled evaluation of data completeness reports will trigger protocols for tracking and obtaining missing data. In our previous research, we developed patient tracking and communication protocols that resulted in very low rates of missing data. These field tested procedures with proven effectiveness, with the necessary site specific adjustments, will be disseminated across all study sites.

12.11 Controlling Type 1 Error in Primary Analyses

In this study, we have defined two primary aims, one for implementation and one for efficacy. As this study is designed as a Hybrid Type 3 Effectiveness-Implementation study, the implementation is the main outcome, and so when measuring success of the study, the implementation outcome will take precedent over the effectiveness outcome, which will be considered secondary. Therefore, considering the effectiveness aim as secondary, it is not necessary to put in procedures to control the type 1 error across multiple outcomes. We also do not anticipate multiple-comparison adjustments when performing secondary analyses, but instead will be mindful of the multiple testing problem, thus report secondary findings as noteworthy hypothesis-generating results only when their p-values are considerably smaller than 0.05.

12.12 Interim Monitoring

No interim looks at primary or secondary outcomes are planned for this study. However, a power and sample size recalculation will be performed based on the primary outcome rates and enrollment rates observed in the baseline evaluation period. The power and sample size recalculation will be done no earlier than the end of the first site's baseline evaluation period.

12.13 Planned Secondary Analyses

We plan to perform the following secondary analyses:

Implementation Outcomes to compare the baseline evaluation and IF evaluation periods.

- Fidelity to a critical action checklist relating to the provision of ED-initiated BUP with referral for ongoing MAT in eligible patients
- Rates of enrolled patients with OUD receiving an appointment for opioid treatment provider/program upon ED discharge
- Number of ED providers receiving DATA 2000 training
- Number of clinicians providing ED-initiated BUP with referral for ongoing MAT
- ED provider readiness and preparedness ruler scores to initiate BUP and provide referral for ongoing MAT
- ED Organizational Readiness to Change Assessment (ORCA) scores relating to ED-initiated BUP with referral for ongoing MAT

- Community opioid treatment provider/program readiness and preparedness ruler scores to continue MAT for patients with OUD who have received ED-initiated BUP
- Community opioid treatment provider/program Organizational Readiness to Change Assessment (ORCA) scores relating to receiving patients with OUD who have received ED-initiated BUP.

Effectiveness Outcomes to compare the baseline evaluation and IF evaluation periods:

- Self-reported days of illicit opioid use (past 7-days) as measured by TLFB methods at 30 days
- Overdose events (past 30 days) captured by participant self-report, state medical examiner records, National Death Index and review of medical records.
- HIV risk taking behaviors (past 30 days) as measured by HIV Risk Taking Behavior Score
- Healthcare service utilization (past 30 days) measured by Health Services Utilization Form
- Rates of illicit opioid negative urines at 30 days

Data for the secondary implementation and effectiveness outcomes will be collected by trained RAs and using standardized assessment instruments (see Table 2) via face to face interviews with ED providers and patients with OUD enrolled in the proposed implementation research. The RAs will use tablet based software application to read questions and record responses directly to Advantage eClinical. Urine drug screen results will be obtained by testing urine samples using instant/rapid tests and entering the test result directly into Advantage eClinical via the tablet software application.

12.14 Statistical Methods

12.14.1 Primary Outcome Analysis

The study primary outcome is the implementation outcome. This outcome is defined as the rate of ED-initiated BUP with referral for ongoing MAT. The following base model will be used to compare the IF evaluation period to the baseline evaluation period in regards to the rates of ED-initiated BUP with referral for ongoing MAT.

$$\text{logit}(p_{si}) = \alpha + \beta t_{si} + \gamma f_{si} + r_s$$

where:

p_{si} is the probability of success of patient i at site s .

t_{si} is the calendar time of enrollment of patient i at site s . In the simulations reported below, t is expressed in integer months.

f_{si} is the indicator of whether patient i at site s is in the baseline ($f=0$) or IF ($f=1$) periods

r_s is the random effect of site s , where $r_s \sim N(0, \sigma)$

The following SAS code fragment estimates this model:

```
proc glimmix data = simul method = quad;
class arm (ref="1");
model z / trials = arm month / dist = binomial link = logit solution;
random intercept / subject = site;
estimate "trt effect" arm 1 -1 / cl;
lsmeans arm / cl ilink;
run;
```

In this model the γ estimate represents the estimated difference in the logit of the probability of success. The model will test a one-tailed hypothesis at a 0.05 level. The null and alternative hypotheses are:

$$H_0: \gamma = 0$$

$$H_a: \gamma > 0.$$

12.14.2 Effect Modification of Primary Analysis

Several covariates may have an effect on the primary outcome. At a minimum, sex, race and ethnicity will be considered as covariates in the model. They will be entered into the model in a stepwise manner using a p-value cutoff of 0.05. The most complicated model with the three minimal covariates would be:

$$\begin{aligned} \text{logit}(p_{si}) = & \alpha + \beta t_{si} + \gamma f_{si} + \theta_1 * \text{sex}_{si} + \theta_2 * \text{race}_{si} + \theta_3 * \text{ethnicity}_{si} \\ & + \theta_4 * f_{si} * \text{sex}_{si} + \theta_5 * f_{si} * \text{race}_{si} + \theta_6 * f_{si} * \text{ethnicity}_{si} + r_s \end{aligned}$$

where sex, race and ethnicity are indicators for their respective variables. Additional appropriate covariates and parameters may also be considered in the above model.

12.14.3 Secondary Implementation Outcomes

- Fidelity (as measured by the check list score) to a critical action checklist relating to the provision of ED-initiated BUP with referral for ongoing MAT in eligible patients will be compared in the IF evaluation period to the baseline evaluation period. This will be done using standard models including mixed models, or other appropriate methodology.

- Rates of enrolled patients with OUD receiving an appointment for opioid treatment provider/program upon ED discharge. The IF evaluation period will be compared to the baseline evaluation period using the model described for the primary analysis in section 12.14.1.
- Number of ED providers receiving DATA 2000 training will be compared between IF evaluation period and baseline evaluation period using appropriate methodology. Permutation tests will be considered for this analysis.
- Number of clinicians providing ED-initiated BUP with referral for ongoing MAT will be compared in the IF evaluation period to the baseline evaluation period using count models. Models considered will be Poisson, zero-inflated Poisson, negative binomial and zero-inflated negative binomial. An offset will be considered for how long the provider has been trained.
- ED provider readiness and preparedness ruler scores to initiate BUP and provide referral for ongoing MAT will be compared between IF evaluation period and baseline evaluation period. This will be done using standard models including mixed models or other appropriate methodology. If the data do not follow a Gaussian distribution a modified Wilcoxon test ⁵⁸ will be used.
- ED Organizational Readiness to Change Assessment (ORCA) scores relating to ED-initiated BUP with referral for ongoing MAT will be compared between IF evaluation period and baseline evaluation period. This will be done using standard models including mixed models or other appropriate methodology. If the data do not follow a Gaussian distribution a modified Wilcoxon test will be used.
- Community opioid treatment provider/program readiness and preparedness ruler scores to continue MAT for patients with OUD who have received ED-initiated BUP will be compared between IF evaluation period and baseline evaluation period. This will be done using standard models including mixed models or other appropriate methodology. If the data do not follow a Gaussian distribution a modified Wilcoxon test will be used.
- Community opioid treatment provider/program Organizational Readiness to Change Assessment (ORCA) scores relating to receiving patients with OUD who have received ED-initiated Bup will be compared between IF evaluation period and baseline evaluation period. This will be done using standard models including mixed models or other appropriate methodology. If the data do not follow a Gaussian distribution a modified Wilcoxon test will be used.

12.14.4 Effectiveness Outcomes

- The primary effectiveness outcome is defined as the rates of patient engagement in formal addiction treatment on the 30th day post enrollment. The model described in section 12.14.1 and 12.14.2 will be used to analyze this outcome.
- Self-reported days of illicit opioid use (past 7-days) as measured by TLFB methods at 30 days will be compared between IF evaluation period and baseline evaluation period using count models. Models considered will be Poisson, zero-inflated Poisson, negative binomial and zero-inflated negative binomial.

- Overdose events (past 30 days) captured by participant self-report, state medical examiner records, National Death Index and review of medical records will be compared using count models. Models considered will be Poisson, zero-inflated Poisson, negative binomial and zero-inflated negative binomial. An offset will be considered for how long a participant was in a given period if less than 30 days.
- HIV risk taking behaviors (past 30 days) as measured by HIV Risk Taking Behavior Score will be compared between IF evaluation period and baseline evaluation period. This will be done using standard models such as mixed models or other appropriate methodology. If the data do not follow a Gaussian distribution a modified Wilcoxon test will be used.
- Healthcare service utilization (past 30 days) measured by Health Services Utilization Form will be compared using count models. Models considered will be Poisson, zero-inflated Poisson, negative binomial and zero-inflated negative binomial. An offset will be considered for how long a participant was in a given period if less than 30 days.
- Rates of illicit opioid negative urines at 30 days. The IF evaluation period will be compared to the baseline evaluation period using the model described for the primary analysis in section 12.14.1.

For all secondary analyses, covariates such as sex, race and ethnicity will be considered if appropriate and feasible. Specifically, if model based approaches are used covariates will be considered. If non-parametric methods are used then the tests may be done at different covariate levels.

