9.0 STUDY PROCEDURES

9.1 Screening and Informed Consent Procedures Baseline and IF Evaluation Periods

9.1.1 Screening

Patients will be recruited throughout the entire evaluation period at each ED site. Research Associates (RAs) assigned to the study will work in shifts to ensure cross coverage to screen all ED patients who are potentially eligible for the study. The RA will use the ED log to identify all patients seen in the ED and will eliminate patients with obvious exclusions such as under police custody. The RA will keep a log of all patients excluded and the reasons for exclusion. Patients will be evaluated by an RA for eligibility.

Patients will be asked for verbal consent to complete a set of screening assessments starting with a screener that includes questions about illicit opioid use in the past 30 days embedded in a general health and substance use screener that also includes questions about safety, tobacco and alcohol use.^{25,26} We have successfully used this strategy of embedding questions about opioid use in a general health survey as a method to screen for drug and alcohol use. Embedded questions have also been noted by the World Health Organization to improve the reliability of self-reported behavior. The screener will contain questions regarding heroin/fentanyl and non-medical use of prescription opioids (ED Health Quiz screener).

Potential study patients who report any opioid use in the past month will complete a 7-day TLFB. If opioid use is reported during the past 7 days a brief (10 minute) structured diagnostic interview (DSM-5) to evaluate for the presence of moderate/severe OUD is administered. Potential study patients who do not meet criteria for moderate/severe OUD will not be asked to participate and will be given a handout recommending that they abstain from drug use and a list of local referral options at the discretion of their ED providers. Those who meet criteria for moderate/severe OUD will be informed that they may qualify for a study if they are willing to produce a urine sample. If the urine tests are positive for any opioid (*fentanyl only are not eligible*), the patient indicates he/she is able to provide contact information for 2 reliable contacts and the patient meets all eligibility criteria on the Patient Participant Eligibility Summary form, patients will be offered participation and informed consent will be obtained.

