10.2.8 Timeline Follow-back (TLFB)

The Timeline Follow-back procedure (Sobell & Sobell, 1992²⁸; Fals-Stewart, 2000³⁴) will be used to elicit the patient participant's self-reported use, quantity, and route of administration of opioids, marijuana, stimulants, benzodiazepines and alcohol. At enrollment, substance use is reported by the patient participant for the 7-day period prior to informed consent.²⁸ At the 30 day follow-up visit, substance use is reported for the 7 days prior to study day 30.

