7.6.2 Secondary Effectiveness Outcomes

1. Self-reported days of illicit opioid use (past seven-days) as measured by TLFB method at 30 days: The following substances collected on TLFB method will be considered illicit opioid use if there is no prescription: heroin, oxycodone, hydrocodone, fentanyl, morphine, hydromorphone, meperidine, methadone, buprenorphine, oxymorphone, pentazocine, and codeine.
2. Overdose events (past 30 days) captured by participant self-report in ODE: The outcome will be scored from question 1 “On how many days in the past 30 days do you think you overdosed on opioids (you used more opioids than you should have used and were more sedated, drugged, or high than you wanted to be)?”
3. HIV risk taking behaviors (past 30 days) as captured in HST.
4. Healthcare service utilization (past 30 days).
5. Rates of illicit opioid negative urines at 30 days as captured on urine drug screen (UDS): A UDS will be considered negative for opioids if all of the following substances are negative: opiates (2000ng), oxycodone, methadone, opiates (300ng), buprenorphine and fentanyl. If a participant tests positive on the UDS for any of these substances and self-reports on TLFB that they have a prescription for any opioid, then the use will be considered licit (i.e., not illicit).

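### Days of illicit opioid use out of 7 are assigned only to unbounded count models, with no robust variance and without naming the 7-day count already collected at enrollment

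*Protocol*

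**What the plan says.** The outcome is a count of days in a fixed week. Protocol 10.2.8 states: "At the 30 day follow-up visit, substance use is reported for the 7 days prior to study day 30". SAP 7.6.2 defines the same outcome ("Self-reported days of illicit opioid use (past seven-days) as measured by TLFB method at 30 days") and lists the substances that count as illicit when there is no prescription, but gives no model.

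The only model statement is in Protocol 12.14.4: "Self-reported days of illicit opioid use (past 7-days) as measured by TLFB methods at 30 days will be compared" between the two periods "using count models. Models considered will be Poisson, zero-inflated Poisson, negative binomial and zero-inflated negative binomial". It gives no rule for choosing among the four, no robust variance, and no site or time term for these models. The urine outcome in the same section is sent to the model of 12.14.1, which has both terms.

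The same measure exists at entry: "At enrollment, substance use is reported by the patient participant for the 7-day period prior to informed consent" (Protocol 10.2.8; Table 2 shows it at enrollment and at 30 days). For all secondary analyses, Protocol 12.14.4 says "covariates such as sex, race and ethnicity will be considered if appropriate and feasible". Baseline opioid days are neither named nor excluded.

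Nothing later replaces this. SAP 1.0 assigns the secondary analyses to the Lead Node, and the Revised SAP section at the end of the SAP changes only the models for the two primary outcomes.

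**The concern.** An outcome limited to 0–7 has a variance tied to its two ends. Participants have moderate to severe opioid use disorder, and screening asks for reported use in the past 7 days. A month later a cluster of abstinent patients and a cluster of daily users is plausible, though no document shows it. A Poisson model sets the variance equal to the mean and cannot describe such data. Negative binomial and zero-inflated models allow for spread or extra zeros, but not for a pile-up at 7.

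The p-values matter even for a secondary outcome. Protocol 12.11 and SAP 9.0 apply no multiplicity adjustment and rely on highlighting only results well below 0.05. If standard errors are understated by 1.46 times, a correct z of 1.96 is reported as 1.96 × 1.46 = 2.86 (p about 0.004). At 1.72 times it becomes 3.37 (p about 0.0007). Either could pass that informal filter.

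The baseline count matters because the periods contain different patients, not individually randomized and enrolled at different calendar times. SAP 5.1 leaves the comparison of their characteristics informal unless differences are suspected.

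**Working it through.** **No planned figure to reproduce.** The documents give no mean, SD, effect size or power for this outcome. Planned enrollment is 4 sites × 120 = 480 per period (Protocol 12.3). The shape of the outcome, the baseline correlation and a two-sided 5% test are assumptions below.

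**Step 1: Poisson, closed form.** For two equal groups with a log link, true SE ÷ model SE = √(variance ÷ mean), whatever the sample size. Put a share *a* at 0, a share *b* at 7, and spread the rest *c* = 1 − a − b evenly over 1–6. Then mean = 7b + 3.5c and variance = 49b + (91/6)c − mean². Size is 2 × P(Z > 1.96 ÷ ratio).

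| a at 0 | b at 7 | Mean | Variance | Variance ÷ mean | SE ratio | Size |
|---|---|---|---|---|---|---|
| 25% | 20% | 3.325 | 7.09 | 2.13 | 1.46 | 17.9% |
| 25% | 45% | 4.20 | 8.96 | 2.13 | 1.46 | 18.0% |
| 40% | 20% | 2.80 | 8.03 | 2.87 | 1.69 | 24.7% |
| 40% | 45% | 3.675 | 10.82 | 2.94 | 1.72 | 25.3% |

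**Step 2: other shapes.** For a general 0–7 outcome, variance = μ(1 − μ/7)(1 + 6ρ), with ρ from 0 (binomial) to 1 (everyone at 0 or 7). The Poisson SE ratio then runs from 0.85 to 2.24 at a mean of 2 days, 0.71 to 1.87 at 3.5, and 0.53 to 1.41 at 5. Simulated beta-binomial data (480 per period, no effect, no site or time effect, 500 replicates) give:

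| Mean, ρ | Poisson SE ratio | Poisson size |
|---|---|---|
| 2, 0.3 | 1.40 | 16.4% |
| 2, 0.7 | 1.97 | 32.0% |
| 3, 0.5 | 1.43 | 18.0% |
| 4, 0.7 | 1.51 | 19.0% |
| 5, 0.5 | 1.03 | 5.8% |
| 5, 0.1 | 0.70 | 0.6% |

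**Step 3: the other listed models.** In the overdispersed shapes, negative binomial had an SE ratio of 0.71–0.94 and a size of 0.8–3.2% (250 replicates). With 35% at 0 and 35% at 7 it rejected less than 1% of the time. The cause is the dispersion estimate. Per group, the model variance of the log mean is (1/μ + α)/n. In this shape μ = 3.5 and variance = 17.15 + 4.55 − 12.25 = 9.45, so the α that matches the variance is (9.45 − 3.5)/12.25 = 0.49. In a simulation check, maximum likelihood settled near 1.22, which gives √[(0.286 + 0.486)/(0.286 + 1.22)] = 0.72. At a mean of 5 with ρ of 0 or 0.1, 130 and 149 of 250 negative binomial fits failed. Zero-inflated Poisson had SE ratios of 0.54–1.16 and size of 0–10%, and its count-part coefficient does not describe mean days. Zero-inflated negative binomial was not simulated.

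**Step 4: the alternative.** Quasi-binomial on days ÷ 7 gave SE ratios of 0.95–1.04 and size of 3.0–6.6% in all nine shapes tried (500 replicates, Monte Carlo error about 1 point). Poisson with robust standard errors gave 0.96–1.04 and 3.6–6.8% (250 replicates).

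**Step 5: baseline adjustment.** The standard error falls by 1 − √(1 − r²): 1 − √0.91 = 4.6% at r = 0.3, and 1 − √0.75 = 13.4% at r = 0.5.

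**The case against.** The plan says the four models will be considered; being listed first does not commit the analyst to Poisson, and a careful analyst would notice overdispersion. That stands: the 18–25% figure applies only to a Poisson fit with model-based standard errors on U-shaped data. But the usual step, to negative binomial, tends to err the other way, and the plan has no selection rule.

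A reader might infer that model probability above 7 biases the estimated effect. In a two-group Poisson or negative binomial fit without covariates it does not, because the fitted means equal the sample means. The problem is the variance, and robust standard errors would repair a Poisson fit too. A bounded model is therefore preferable but not the only remedy.

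A reader might also infer that the plan rules out baseline or site adjustment. It does not. The covariate list is open-ended, and no linear predictor is written for any of the count models. This is an omission, not an exclusion. The gain in precision is also modest: screening on recent use confines baseline opioid days to about 1–7, which may hold the correlation down.

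Finally, enrollment ended in October 2020 (SAP 3.3.6) and the Revised SAP already reports a primary effectiveness result, so a change now may be post hoc.

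**Conclusion.** The concern holds in a limited form. The only models named for an outcome restricted to 0–7 are unbounded, no robust variance is given, and an available baseline value is not named.

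The size of the error depends on assumptions. For the assumed U-shapes, model-based Poisson standard errors are about 1.5–1.7 times too small, with size of about 18–25% at nominal 5%, while negative binomial is usually too wide. For a mean near 5 days Poisson can be about right or conservative. The documents therefore do not support a general claim that the planned analysis inflates false positives, or any single direction of error. What can be said is that none of the three listed models that were simulated had reliable error bars across the shapes tried, while the bounded alternative did.

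The precision gain from baseline days rests on an assumed correlation and is small at 0.3 or below; case-mix adjustment between non-randomized cohorts is the further reason to include it. The point concerns one of five secondary effectiveness outcomes, treated as hypothesis-generating. It does not touch the primary implementation or primary effectiveness conclusions.

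**What to change.** In SAP 7.6.2, replace the menu for this outcome with one model for days out of 7: beta-binomial, or fractional logit (quasi-binomial) with robust standard errors. Include period, site and the enrollment 7-day illicit opioid count, scored by the same rule as at day 30. State that model-based Poisson standard errors will not be used, and report the difference in mean days with its interval.

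The cost is a wording change and a short program; the data are already collected. The documents do not say whether this outcome has been analysed. If it has not, date the change before the analysis. If it has, report the bounded model as a post hoc reanalysis beside the original result.

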7.2 Exclusion Criteria

All patients enrolled into the study must not:

1. Have a medical or psychiatric condition that requires hospitalization at the index ED visit
2. Be actively suicidal or severely cognitively impaired precluding informed consent
3. Present from extended care facility (e.g., skilled nursing facility)
4. Require continued prescription opioids for a pain condition
5. Be a prisoner or in police custody at the time of index ED visit
6. Currently have (past 30 days) enrolled in formal addiction treatment, including by court order
7. Inability to provide reliable locator information including 2 contact numbers
8. Be unwilling to follow study procedures (e.g., unwilling to provide permission to contact referral provider/program or return for 30-day assessment)
9. Have prior enrollment in the current study

Note: A patient may **NOT** enroll in both the baseline evaluation and IF evaluation periods.

10. Not able to speak English sufficiently to understand the study procedures and provide written informed consent to participate in the study

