10.2.9 Health Services Utilization Inpatient and Health Services Utilization Outpatient²⁹

A brief, structured interview regarding health care utilization (inpatient and outpatient) will be used, which collects information on the type and amount of services received. This includes ED visits, hospitalizations, primary medical care visits (excluding those for buprenorphine treatment and self-help sources of support (e.g., NA)). It is collected at enrollment and at 30 days post study enrollment.

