10.2.10 Health Status

The Health Status form collects information on HIV and Hepatitis C status, HIV risk (CTN HRBS), Pain (PEG), and psychological health (PHQ-9)³¹ usual care and reason for ED visit. The HIV Risk-taking Behaviour Scale (HRBS)³² is a brief, 12-item questionnaire measuring the behavior of people who inject drugs that puts them at risk of either contracting/transmitting HIV. Also embedded within is the Patient Health Questionnaire (PHQ-9)³¹ used to assess depressive symptoms. Health status questions are collected at enrollment and at 30 days post study enrollment.

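### The patient's enrolment value is not prespecified as a covariate for the Day-30 HIV risk score and healthcare-use comparisons, although the same forms are completed at enrolment

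*Protocol*

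**What the plan says.** **Analysis.** Protocol 12.14.4 states that HIV risk taking "as measured by HIV Risk Taking Behavior Score will be compared between IF evaluation period and baseline evaluation period", by mixed models or another suitable method. Its fallback is: "If the data do not follow a Gaussian distribution a modified Wilcoxon test will be used". For service use it states: "Healthcare service utilization (past 30 days) measured by Health Services Utilization Form will be compared using count models". Four candidate count models are listed, with a possible offset for short observation time. The only statement on adjustment is: "For all secondary analyses, covariates such as sex, race and ethnicity will be considered if appropriate and feasible". The same paragraph allows non-parametric tests to be run within covariate levels.

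**SAP.** Section 7.6.2 gives "HIV risk taking behaviors (past 30 days) as captured in HST" as item 3 and only a label for healthcare use as item 4. Neither item has a model or a covariate.

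**Collection.** The HRBS sits on the Health Status form, and Protocol 10.2.10 says: "Health status questions are collected at enrollment and at 30 days post study enrollment". Of the Health Services Utilization interview, Protocol 10.2.9 says: "It is collected at enrollment and at 30 days post study enrollment". Protocol Table 2 shows the same schedule in both periods.

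**Who is compared.** Protocol 7.2 says: "A patient may NOT enroll in both the baseline evaluation and IF evaluation periods". SAP 2.3.3 confirms that there is no randomisation of participants. SAP 5.1 expects similar cohorts and, where a difference is suspected, provides for a statistical test. It says nothing about adjustment. The SAP Table 11 shell tabulates enrolment inpatient and outpatient counts but not the HRBS score.

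**The concern.** The period contrast for these outcomes compares two separate groups of patients enrolled at different calendar times. The same measure taken on the same patient a month earlier is likely to be the best single predictor of the Day-30 value. It is already in the database, yet no section of either document assigns it to the analysis.

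Two things follow if the comparison is run without it. First, between-patient variation that the enrolment value could explain stays in the error term. Second, if the cohorts differ at entry in injecting risk or service use, part of that difference would appear in the period contrast.

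The documents give reasons why case mix could shift. Protocol 11.10 describes marketing to patients and community referrers once the IF period is complete. SAP 3.3.6 records COVID-19 enrolment pauses at two sites, both within the IF evaluation period. These show that a shift is possible, not that one occurred. Because Table 11 omits the HRBS score, an imbalance in it would not be seen there.

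**Working it through.** The documents give no standard deviation, target effect, power or enrolment-to-Day-30 correlation for either outcome, so there is no figure of the plan's own to reproduce. The calculation below is for the HIV score only.

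**From the documents**
- Protocol 12.3 plans about 120 patients per site per period at 4 sites: 120 × 4 = 480 per period.

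**Assumed**
- Correlation r between enrolment and Day-30 score: 0.3, 0.5 or 0.7.
- Gaussian outcome, no site clustering, complete follow-up.
- Two-sided 0.05 test. The documents set no level or sidedness for these outcomes.
- A starting power of 80% for the unadjusted comparison.

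**Precision**
- Variance factor with the enrolment score as covariate: 1 − r².
- Equivalent sample size per period: 480 / (1 − r²).
- Power after adjustment: Φ((1.96 + 0.842) / √(1 − r²) − 1.96).
- Difference detectable with 80% power, unadjusted: 2.80 × √(2/480) = 0.181 SD. Adjusted: 0.181 × √(1 − r²).

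| r | Variance factor | Equivalent n per period | Power (from 80%) | Detectable difference (from 0.181 SD) |
|---|---|---|---|---|
| 0.3 | 0.91 | 527 | 84% | 0.173 |
| 0.5 | 0.75 | 640 | 90% | 0.157 |
| 0.7 | 0.51 | 941 | 98% | 0.129 |

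Worked row, r = 0.5: 2.802 / 0.866 − 1.96 = 1.275, and Φ(1.275) = 0.90.

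With an assumed 80% follow-up, n is 0.8 × 480 = 384 per period. The detectable difference is then 0.202 SD unadjusted and 0.193 / 0.175 / 0.144 adjusted. The variance factor does not depend on n.

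**Carried-over entry difference**

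If the cohorts differ by d SD at enrolment and the true IF effect is zero, the unadjusted contrast has expectation r × d. With d = 0.2 (assumed) this is 0.06 / 0.10 / 0.14 SD. A simulation with 480 per period and 4,000 runs gave:

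| r | d | Unadjusted: bias (SD) | Unadjusted: rejection | Adjusted: bias (SD) | Adjusted: rejection |
|---|---|---|---|---|---|
| 0.3 | 0.2 | 0.061 | 16% | 0.001 | 5% |
| 0.5 | 0.1 | 0.050 | 12% | 0.001 | 5% |
| 0.5 | 0.2 | 0.099 | 33% | −0.001 | 4% |
| 0.5 | 0.3 | 0.149 | 63% | 0.000 | 6% |
| 0.7 | 0.2 | 0.140 | 58% | 0.000 | 5% |

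The simulated entry difference lies wholly in the enrolment score. Imbalance in other variables would remain after adjustment.

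**The case against.** **The plan does not exclude the enrolment value.** A reader might infer that it is left out by design. The documents do not support that. The covariate list gives examples only, no model for these outcomes is fixed, and an enrolment score would fit within what is allowed. SAP 7.6.2 defines measures, so covariates would not be expected there. This stands: the defect is lack of prespecification. It still leaves a material choice open after the data are seen, in a comparison of non-randomised cohorts.

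**The hypotheses are not about change.** A reader might justify the adjustment by saying they are. Protocol 4.3.4 states between-period contrasts at the 30-day assessment. The case for adjustment does not need a change hypothesis.

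**No bias is shown.** A reader might conclude that the estimated IF effect is biased. The documents report no entry difference in either measure. Protocol 12.15 and SAP 5.1 plan checks of cohort comparability, which would reveal an imbalance in the characteristics they cover, though they would not correct it.

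**The Gaussian figures do not transfer to utilization.** Those outcomes go to count models, so 1 − r² does not apply directly. Protocol 4.3.4 names inpatient OUD services, while exclusion 6 removes anyone in formal addiction treatment in the past 30 days, which under Protocol 2.1 includes inpatient and residential care. The enrolment predictor for that hypothesis is therefore restricted by design. This stands, and no gain is claimed for it.

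**The fallback is ambiguous.** A reader might say the modified Wilcoxon test ignores enrolment values. Protocol 12.14.3 cites for it a signed-rank method for clustered data, which works on paired differences, whereas the stated comparison is between different patients. What the test would be applied to is unclear.

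**The gain may be small.** At r = 0.3 it is about 4 percentage points of power; it passes 5 points only at r of about 0.36.

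**Conclusion.** The point holds as a lack of prespecification. Neither Protocol 12.14.4 nor SAP 7.6.2 commits to the enrolment value for the Day-30 HIV risk score or healthcare use, and nothing else in the plan adjusts for a suspected entry difference in these measures.

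For the HIV score the benefit runs from modest to large over the assumed correlations, with the detectable difference falling by about 0.01 to 0.05 SD at 480 per period. Protection against carried-over imbalance matters only if the cohorts differ at entry, and only for imbalance carried by that variable. For utilization counts the size is unknown and may be smaller for inpatient OUD services.

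The stakes are low. Protocol 12.11 and SAP 9.0 treat secondary findings as hypothesis-generating, and the primary conclusions do not depend on them. This is an inexpensive improvement; it does not show that a result is wrong.

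**What to change.** 1. In Protocol 12.14.4 and the SAP, prespecify the enrolment HRBS score as a covariate, with site and period, in the Day-30 HIV risk model. Do the same with the enrolment inpatient and outpatient counts in the respective utilization models.
2. If the HIV score is non-Gaussian, use a baseline-adjusted model with robust or bootstrap standard errors in place of the modified Wilcoxon test.
3. Add the enrolment HRBS score by period to SAP Table 11.
4. Impute missing enrolment values. Do not use a missing-indicator, which can itself bias a comparison of non-randomised groups.
5. If these analyses have already been run, report the adjusted versions labelled as added.

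The cost is one term in the HIV risk model, the enrolment counts in the utilization models, one table row and an imputation rule. The data come from forms already scheduled at every enrolment visit.
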